5.3 Subject Population(s) for Analysis

All subjects who wore the device for the duration of procedure will be included in the analysis.

6 Safety and Adverse Events

Patients will be undergoing endoscopic procedures that are clinically indicated with inherent risk of the procedure itself. There will be minimal additional risk with placement of a smart device in the pre-operative area. Wearable technologies (eg. smartphones, smart watches) are already permitted in the endoscopy suite, so this protocol would not significantly alter standard of care. Therefore, this study will not track any adverse events.

Definitions

Adverse Effect (Event)

Any untoward medical occurrence in a subject involved in clinical study of an investigational device; regardless of the causal relationship of the problem with the device or, if applicable, other study related treatment(s).

Life-threatening adverse effect: Any adverse effect that places the subject, in the view of either the investigator or the sponsor, at immediate risk of death from the effect **as it occurred**. It does not include a reaction that, had it occurred in a more severe form, might have caused death.

Serious adverse effect: An adverse effect is considered “serious” if, in the view of either the investigator or the sponsor, it results in any of the following outcomes:

- death
- a life-threatening AE
- inpatient hospitalization or prolongation of existing hospitalization
- a persistent or significant disability/incapacity
- a congenital anomaly/birth defect.

Unanticipated adverse effect: Any adverse effect, the nature, specificity, severity, or frequency of which is not consistent with the risk information in the clinical study protocol or elsewhere in the current IDE application.

All inclusion and exclusion criteria are set out and there will be no protocol deviation.

7 Data Handling and Record Keeping

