2.2 Secondary Objective

1. Assess patient and provider preferences regarding wearable technology
2. Outline current practices and policies regarding wearable devices at Mayo Clinic

3 Study Design

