3.4 Primary Safety Endpoints

There are no specific primary safety endpoints pertaining to the study given the non-invasive intervention. Wearable technology like smart watches and smart phones are already permitted within the procedural area.

4 Subject Selection, Enrollment and Withdrawal

All patients who are undergoing gastrointestinal endoscopic procedures with sedation may be eligible for the study. It is anticipated that we will screen up to 1000 subjects and enroll 500 subjects to the study.

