4.4 Early Withdrawal of Subjects

4.4.1 When and how to Withdraw Subjects

The subjects will undergo the clinically indicated procedure with the wearable devices. Early withdrawal would include removal of the devices prior to procedure completion, which can be performed at the discretion of the patient or clinical providers at any point.

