4.4.2 Data Collection and Follow-up for Withdrawn Subjects

Withdrawn subjects will be recorded in the study record in order to calculate the withdrawal rate. There will be no further utilization of any subject related data.

5 Statistical Plan

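### Patients who have a device removed early cannot contribute to the patient-preference results, so reported views are likely, though not certainly, somewhat too favourable

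*Combined protocol and SAP*

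**What the plan says.** Section 2.2 lists as its first secondary objective: "Assess patient and provider preferences regarding wearable technology". Sections 3.1 and 3.3.3 send patients an electronic survey the day after the procedure and keep it open until day 14. Neither section makes the invitation depend on how long the devices were worn. Providers get their own survey at study completion.

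Section 4.4.1 defines withdrawal through the devices: "Early withdrawal would include removal of the devices prior to procedure completion". Removal "can be performed at the discretion of the patient or clinical providers at any point".

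Section 4.4.2 says what is kept on these subjects: "Withdrawn subjects will be recorded in the study record in order to calculate the withdrawal rate". It then adds: "There will be no further utilization of any subject related data". It does not mention recording who removed the device or why.

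Section 5.3 describes the study's only analysis population: "All subjects who wore the device for the duration of procedure will be included in the analysis". It does not mention the survey.

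Section 5.2 leaves subjects with missing or incomplete data out of the final analysis, but promises to report whatever is available on them separately, so that external validity can be judged.

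**The concern.** A patient who finds the watch or the torso device uncomfortable or intrusive, and has it taken off, has given direct evidence on patient preference. Under section 4.4.2 that patient's opinion cannot be used. Entry to the patient-preference sample then depends on something close to the outcome being measured, and this follows from a stated rule rather than from missing detail.

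At stake is how far the patient results can be taken as the views of those who agreed to wear a device. As written, they describe those who agreed and also kept it on to the end. If the rule stays, the lost answers cannot be recovered at analysis. The withdrawal rate will show how many were lost, but not what they thought or whether the patient or a provider made the decision.

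**Working it through.** **Step 1: does the rule reach the survey?**

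- Section 4.4.1: removal before the procedure ends is withdrawal. The text does not say whether taking off one of the two devices counts; the argument needs only that some removals do.
- Sections 3.1 and 3.3.3: the survey opens the day after the procedure, so a remover's answers always come after withdrawal.
- Section 4.4.2: no further use of the subject's data. Whether this covers all the subject's data or only data arising after withdrawal, the survey falls under it.
- Section 5.3: no survey population is defined that would override the bar.

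The exclusion thus rests on sections 4.4.1 and 4.4.2. Section 5.3 matters because it provides no exception.

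**Step 2: do other sections restore these patients?**

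Section 5.2 promises separate reporting for subjects with missing or incomplete data. If removers are among them, sections 5.2 and 4.4.2 contradict each other. If they are not, section 5.2 does not help. Section 7.1 treats revoking authorization as a separate act and even then allows use of information already collected. Taking off a watch revokes nothing, yet section 4.4.2 bars use of the subject's later answers.

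**Step 3: how large could the effect be?**

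The plan gives no figure to reproduce: no removal rate, no survey response rate and no expected level of favourable views. What follows is a bound on assumed inputs.

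- a = share favourable among full wearers (assumed 80%)
- b = share favourable among removers (assumed 0%, 40% or 80%)
- w = share of enrolled patients who have a device removed (assumed 1% to 10%)
- Full wearers and removers are taken to answer the survey at the same rate.

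All enrolled = (1 − w)a + wb, so overstatement = a − [(1 − w)a + wb] = w(a − b).

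| w | removers among 500 | b = 0% | b = 40% | b = 80% |
|---|---|---|---|---|
| 1% | 5 | 0.8 points | 0.4 | 0 |
| 2% | 10 | 1.6 | 0.8 | 0 |
| 5% | 25 | 4.0 | 2.0 | 0 |
| 10% | 50 | 8.0 | 4.0 | 0 |

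Example: w = 5%, b = 0% gives 0.95 × 80% + 0.05 × 0% = 76%, against 80% reported, a gap of 4 points.

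Varying a with b = 0%: at 5% removal the bound is 3.5 points (a = 70%) or 4.5 (a = 90%); at 10% it is 7.0 or 9.0. If removers were more favourable than full wearers, w(a − b) would be negative and the results would be understated.

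**The case against.** The strongest reply is that the effect is probably small and its direction is not shown. Devices go on before sedation and come off when the procedure ends, so an alert patient has limited time to object. Clinical providers may also remove a device for reasons unrelated to the patient's opinion. Both points stand. They are why the bias is called likely rather than established, and why it is given as a bound.

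A second reply is that section 5.3 was written for the accuracy analyses. That is a fair reading: section 5.2 specifies only event concordance and differences in maximum and minimum readings, for which full wear is a natural condition. It does not rescue the survey, because section 4.4.2 bars the data regardless.

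Third, section 3.1 describes the preference work as narrative and qualitative, so no percentage favourable is planned. This also stands. The percentages above only illustrate scale; leaving out dissatisfied patients affects a narrative summary too.

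A reader might go further and infer any of the following, none of which the documents support:

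- *The whole preference objective is compromised.* Providers are surveyed separately, with no condition tied to device wear.
- *Removal is hidden.* The withdrawal rate will be calculated.
- *A policy conclusion about preferences would be distorted.* The policy statements in sections 1.4.1 and 1.4.3 follow remarks on accuracy, interference and inaccurate readings, not the preference survey.
- *Patients who decline to enrol add a much larger bias.* Section 4 expects that "we will screen up to 1000 subjects and enroll 500 subjects", but the up to 1000 − 500 = 500 not enrolled may include ineligible patients and people refusing for reasons unrelated to the devices. Section 3.3.3 directs the survey at patients' experience, and decliners have no experience of the study devices. Any figure would come entirely from the assumed number and views of decliners.

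**Conclusion.** The point holds for the patient part of secondary objective 1. Sections 4.4.1 and 4.4.2 together exclude removers' survey answers, and section 5.3 makes no exception. The patient results are likely, not certainly, more favourable than the views of all who agreed to wear a device.

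The size is unknown. On an assumed 80% favourable among full wearers and equal survey response, the overstatement is at most 4 points at 5% removal and 8 points at 10%, and zero if removers think as full wearers do. The removal rates are assumptions too.

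This is a modest defect in a secondary objective of a descriptive study. It deserves correction because the cause is an explicit rule, the survey already exists and the change is cheap. Sections 4.4.2 and 5.2 need reconciling in any case. The lack of decliners' views is a limit on whom the results describe, not a defect of this analysis.

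**What to change.** 1. In section 5.3, add a patient-survey population: all consented subjects in whom a device was placed, whatever the wear duration. As far as this point is concerned, the full-wear population can stay for the device-accuracy analyses.
2. In section 4.4.2, allow the survey and the reason for removal, including whether the patient or a provider decided, to be used unless the patient withdraws permission for data use.
3. Reconcile sections 4.4.2 and 5.2 by stating whether removers are among the subjects whose available information is reported separately.
4. Describe the patient results as applying to patients who consented to wear a device.

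A count of refusals on the screening log would be useful optional context, but it records no preferences and corrects no bias.

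The cost is a few sentences of protocol text and one recorded item for the reason for removal, with no added visits. The downside is that the reported views may be slightly less favourable.

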5.3 SUBJECT POPULATION(S) FOR ANALYSIS	12
6 SAFETY AND ADVERSE EVENTS	12
7 DATA HANDLING AND RECORD KEEPING	13
7.1 CONFIDENTIALITY.....	13
7.2 SOURCE DOCUMENTS.....	13
7.3 RECORDS RETENTION	14
8 STUDY MONITORING, AUDITING, AND INSPECTING	14
8.1 STUDY MONITORING PLAN	14
8.2 AUDITING AND INSPECTING	15
9 ETHICAL CONSIDERATIONS.....	15
10 STUDY FINANCES	15
10.1 FUNDING SOURCE	15
11 PUBLICATION PLAN	15

12	REFERENCES	15
13	ATTACHMENTS	ERROR! BOOKMARK NOT DEFINED.

LIST OF ABBREVIATIONS

CFR	Code of Federal Regulations
CRF	Case Report Form
DSMB	Data and Safety Monitoring Board
FDA	Food and Drug Administration
GCP	Good Clinical Practice
HIPAA	Health Insurance Portability and Accountability Act
IRB	Institutional Review Board
PHI	Protected Health Information
PI	Principal Investigator
SAE	Serious Adverse Event/Serious Adverse Experience
SOE	Schedule of Events
SOP	Standard Operating Procedure
IQR/M	Interquartile Range/Median

Study Summary

Title	A Prospective Study of the Role and Accuracy of Consumer-Facing Wearable Technology for Patient Monitoring in Gastrointestinal Endoscopy
Running Title	Wearable Technology Endoscopy
Title Acronym	Wearable Tech
IRB Protocol Number	21-007738
Phase	Prospective study
Methodology	Subjects who are eligible will have two consumer-facing wearable smart devices placed before scheduled endoscopy. Data from the devices will be downloaded after the procedure and analyzed. Patients and providers will complete a survey regarding their experience.
Overall Study Duration	6 months Recruitment and Active study execution, 3 months analysis and 3 months publication. Total: 12 months
Subject Participation Duration	Up to 60 days screening prior to study procedure, duration of the procedure itself, and completion of a survey within 14 days of procedure date
Objectives	Measure the accuracy and safety of wearable technology in patients undergoing endoscopic gastrointestinal procedures with sedation. Assess patient and provider preferences regarding wearable technology.
Number of Subjects	Five hundred (500)
Diagnosis and Main Inclusion Criteria	Subjects over 18 years of age who are scheduled to undergo an endoscopic procedure with sedation
Study Device	Consumer-facing wearable smart devices(examples include Apple Watch Series 6, FitBit Versa, The QardioCore ECG ambulatory monitoring device)
Reference Modality	Sedation/Anesthesia record

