1.1 Background

The term wearable technology encompasses a wide spectrum of devices worn on or near a person. (1) Market research suggests that one in five Americans are users of wearable technology with the market currently valued at over 30 billion dollars annually. (2,3) These devices have the ability to record physical information, ranging from heart rate to pulse oximetry, as well as audio and video. These devices are often marketed to improve health and well-being, and there has been significant interest in their use to diagnose, monitor and treat disease. (4) However there remain significant issues regarding the use of wearable technology (5). Rigorous studies of consumer-facing products have shown significant issues with accuracy and reliability. (6,7) Beyond simply inaccurate data, there have also been reports of unintended interference from consumer wearables, resulting in disabled clinical devices. (8) This is in addition to questions regarding the medicolegal, ethical and practical implications of recording data, audio, and video during a clinical encounter.

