2.1 Primary Objective

Measure the accuracy of wearable technology for patient monitoring compared to currently used equipment in patients undergoing gastrointestinal endoscopic procedures with sedation

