3.1 General Design

We will perform a prospective, non-blinded, exploratory study to assess the accuracy and safety of smart technology in the endoscopy suite for patients undergoing gastrointestinal endoscopic procedures with sedation. We will also simultaneously perform an assessment of patient and provider preferences using narrative-driven, qualitative evaluation.

Patients will be identified by reviewing daily procedure listings on endoscopy units on Alfred 6, Gonda 2 and Gonda 9. Recruitment will occur over the phone the day prior to a procedure, or the pre-procedure areas on the day of the procedure. Patients who meet inclusion criteria and consent to participation in the study will be provided the smart devices. The devices will be secured to the wrist and torso by study personnel prior to administration of sedatives. The smart watch will be programmed to record respiratory rate, heart rate, and oximetry using native, first party device applications. These applications include *Blood Oxygen* (measures oxygen saturation), *ECG* (records single lead ECG), *Heart Rate* (heart rate), and *Health* (which logs respiratory rate while sleeping). The QardioCore ECG device will measure a single-lead ECG, heart rate, skin temperature, and respiratory rate.

The patient will undergo his or her scheduled procedure. Patients, proceduralists and anesthetists will not be blinded to their enrollment as the devices will be visible. On completion of the procedure, the devices will be removed by the study coordinator and data downloaded onto a central device for analysis. Procedural information will be extracted from the operative note, sedation record, and anesthesia encounter in EPIC. The day after the patient's procedure, a survey will be submitted to them electronically which will remain open until 14 days after

the procedure. Aen electronic reminder will be sent if uncompleted at 7 days, followed by a telephone reminder if not completed at 13 days. There will be no additional patient follow up after completion of the survey. At study completion, a survey will be sent to involved proceduralists and anesthetists.

3.2

Figure 1: Study Design

[figure not shown]

Table 1. Schedule of Events

	Baseline Screening & Enrollment Visit 1 Days -60 to 0	Accrual: Study Intervention Visit 2 Day 0	Patient Survey Visit 3 Day +1 to +14	Provider survey Days 0 to 180
Inclusion/ Exclusion	X	X (if not performed earlier)		
Device(s) Placement/ Recording		X		
Patient Survey			X	

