3.3.3 Survey (Visit 3)

The day after the patient's procedure, a survey will be submitted to them electronically which will remain open until 14 days after the procedure. An electronic reminder will be sent if uncompleted at 7 days, followed by a telephone reminder if not completed at 13 days. There will be no additional patient follow up after completion of the survey. At study completion, a survey will be sent to involved proceduralists and anesthetists. will be provided electronically to patients to assess their satisfaction and opinions regarding their experience.

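### Safety is a stated aim in the Study Summary and 3.1, but no objective, endpoint or data collection serves it, and the safety reviews in 8.1 have no defined input

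*Combined protocol and SAP*

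**What the plan says.** Two places present safety as an aim. The Objectives row of the Study Summary reads "Measure the accuracy and safety of wearable technology in patients undergoing endoscopic gastrointestinal procedures with sedation". Section 3.1 (General Design) describes an "exploratory study to assess the accuracy and safety of smart technology in the endoscopy suite".

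The formal objectives do not follow. Section 2.1 reads "Measure the accuracy of wearable technology for patient monitoring compared to currently used equipment", with no mention of safety. Section 2.2 lists patient and provider preferences and then "Outline current practices and policies regarding wearable devices at Mayo Clinic".

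On endpoints and data collection, section 3.4 states "There are no specific primary safety endpoints pertaining to the study given the non-invasive intervention". Section 6 argues that a wearable adds minimal risk and that such devices are already allowed in the suite, and concludes "Therefore, this study will not track any adverse events". It then defines adverse, life-threatening, serious and unanticipated effects.

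Section 8.1 schedules a data safety monitoring step after the first subject, at 3 months, and annually if required. Delegated study staff carry out the review, and reports go to the IRB if required.

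**The concern.** A study can report on safety only if it collects something that bears on safety. Here the aim is stated twice, while an explicit rule in section 6 removes the data most directly relevant to it. This is a conflict between stated texts, not a detail left unspecified.

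The protocol raises device concerns of its own. Section 1.4.2 names allergic reaction to the watch or band and infection carried by re-used devices. Section 1.1 cites, as background, "unintended interference from consumer wearables, resulting in disabled clinical devices". No outcome is planned for any of these.

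What is at stake is the claim made at the end. The results are to be published (section 11) and are meant to inform institutional policy (1.4.1 and 1.4.3). A paper that repeats the Summary objective would claim a safety assessment, and the absence of reported events could be taken as evidence of safety when events were simply not collected.

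**Working it through.** The plan gives no safety figure to reproduce, and section 5.1 reports no power analysis. The check is therefore a comparison of texts.

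**Step 1: is safety an aim?** Study Summary: yes. Section 3.1: yes. Sections 2.1 and 2.2: no.

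**Step 2: is there a safety endpoint?** Section 3.4 literally excludes only primary ones. No secondary or exploratory safety endpoint appears elsewhere in the available text.

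**Step 3: could other planned data serve?**

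| Source | What the plan does with it | Named as a safety outcome? |
|---|---|---|
| 5.2 heart-rate, saturation, rhythm and respiratory-rate events | Device-versus-record concordance, which is accuracy | No |
| Patient survey (3.3.3) | "to assess their satisfaction and opinions regarding their experience" | No |
| Provider survey (3.1, 3.3.3) | Provider preferences (2.2) | No |
| Operative note, sedation record, anesthesia encounter (3.1) | Extraction of procedural information | No |
| Early removal (4.4.2) | Counted so that a withdrawal rate can be calculated; no recording of the reason is mentioned | No |
| Reviews in 8.1 | Scheduled, with no safety outcome defined as input | No |

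**Step 4: conclusion from the text.** The stated aim has no designated outcome, and section 6 excludes adverse events as a source.

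**Step 5: scale if recording were added.** This is an illustration, not a property of the current plan. With zero events among n subjects assessed, the exact two-sided 95% upper limit is 1 − 0.025^(1/n). The planned enrolment is 500 (section 4). The smaller values of n are assumptions standing for survey non-response.

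- n = 500: 1 − 0.025^(1/500) = 0.74%
- n = 400: 0.92%
- n = 250: 1.47%
- n = 150: 2.43%

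**Step 6: who would be counted.** Section 4.4.1 defines early withdrawal as device removal before the procedure ends. Section 4.4.2 then bars further use of those subjects' data, and 5.3 analyses those who wore the device throughout. If recording were added and these sections left alone, an event that led to removal would drop out of the count. Two other sections also need to be squared with 4.4.2: 5.2 reports available information on incomplete subjects separately, and 7.1 allows use of information collected before authorization is revoked.

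**The case against.** The strongest reply is that the operative sections agree with one another. Sections 2.1, 2.2, 3.4, 5.2 and 6 describe an accuracy and preference study. Sections 3.4 and 6 give reasons for not following events, and the word safety survives only in a summary table and one design sentence. On that view this is an editorial slip. Much of this stands: the decision in section 6 is reasoned and may be deliberate, and if the sponsor meant no safety aim, the correction is mostly textual. It does not remove the conflict, because the Summary row is itself labelled as objectives and 8.1 still schedules safety reviews.

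A second reply is that the documents do not define safety. It could mean the danger of relying on a device that misses a desaturation, which the 5.2 concordance would touch. That reading is possible, but the plan does not adopt it; 5.2 presents concordance as a comparison with the record.

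Third, the survey instruments, Figure 1 and any attachments could not be examined, so a safety item may exist there. The finding is limited to the available text.

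A reader might also infer more than the documents support:

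- That the accuracy results are compromised. They are not; nothing here touches them.
- That excluding early removals biases a safety rate. The current plan reports no such rate, so the point in step 6 arises only if recording is added.
- That not tracking events is wrong in itself. The protocol justifies that choice; what it does not justify is keeping the aim alongside it.

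**Conclusion.** The inconsistency holds and should be corrected. On the available text, the stated safety aim has neither planned data nor a planned analysis, and the 8.1 reviews have no defined safety input. The accuracy objective is unaffected and no existing estimate is biased, so the defect has no numerical size. The consequence is an unsupported safety claim if the Summary objective is carried into publication.

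Confidence is high for the conflict of wording. It is lower for any statement that no safety information of any kind will exist, because the survey instruments and attachments were not available. The confidence limits in the working describe a hypothetical addition and assume zero events with every counted subject assessed.

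**What to change.** Reconcile the Study Summary and 3.1 with sections 2, 3.4, 6 and 8.1 in one of two ways.

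**(a) Keep the aim.** Add safety to section 2 and replace the section 6 sentence with text such as:

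> Recording is limited to device-related events: skin or allergic reaction at the device site, suspected device-related infection, observed interference with clinical equipment, and early device removal with its reason. Staff enter these at device removal. One item in the day 1 to 14 patient survey asks about later skin reaction or infection. Counts are given with exact 95% confidence intervals among all subjects on whom a device was placed, with the number assessed for each item. These data are the input to the reviews in 8.1.

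Align 3.4 with this. State in 4.4.2 and 5.3 that early-removal subjects count in this summary, subject to consent and consistent with 7.1, and that the accuracy population is unchanged. State how 4.4.2 fits with the separate reporting in 5.2.

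Cost: about four fields in the existing Excel tracking, one survey item and short amendments, using existing staff. Limits: survey non-response, and weak attribution, since self-report cannot show that a later infection came from a re-used device.

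**(b) Drop the aim.** Delete *and safety* from the Study Summary objectives and from 3.1, and make no safety claim in publication. Section 6 and 8.1 cannot simply stay as they are: reconcile the adverse-effect definitions that nothing else in the plan uses, and the scheduled safety reviews, with the decision.

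Cost: a text amendment only, with no change to data collection.
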